#### Statistical methodology:

The data will be expressed with measures of central tendency: mean and standard deviation for the quantitative variables. The qualitative variables will be presented in frequencies and percentages. The statistical analysis will be carried out through the Kruskal-Wallis test for quantitative variables. The difference between the qualitative variables will be analyzed by means of X2 (Chi2). An alpha  $\leq$  0.05 will be considered significant.

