#### 6.6.1 Calculation of the sample size.

Although there are no references on the calculation of sample size in phase I studies, it was considered pertinent to perform it according to the presentation of adverse events reported by Hwang HS, et al, in a case-control study in 150 subjects with ophthalmic solutions with Hyaluronate sodium and diquafosol with and without preservative for 3 months. [46].

The percentage of adverse events that occurred with the preservative-free HS solution was 8%, which is why we consider that at least more than 60% of the exposed subjects will not present this rate of adverse events.

The sample size was calculated using the formula for proportions

$$n = \left[ (p1)(p2) + (p1)(p2) \left( \frac{Z_{1-\alpha}}{2} + Z_{1-\beta} \right)^2 \right] / (p1 - p2)^2$$

With a statistical confidence of 95% corresponding to the type I error, equal to 1.96, with a power of 80%, corresponding to the type II error, equal 0.84.

According to the previous calculation, the result is 7.6 subjects (8) per group. The total when considering 3 intervention groups is 24 subjects, which was increased by 25% due to the probable losses. The total sample size required is 30 subjects. Therefore, each group will consist of 10 subjects, who will provide both eyes for the analysis, so that the total sample to be analyzed will be composed of 60 eyes.

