# 8.3 Statistical methodology

#### 8.3.1 Analysis of primary and secondary outcome variables.

The statistical analysis will be carried out by personnel from Sophia Laboratories, S.A. of C.V The statistical program SPSS version 19 (IBM Corporation, Armonk, NY, USA) will be used.

The designated personnel will be blinded to the intervention groups. The coding will be done using consecutive numbers for each intervention group.

The data will be collected and sorted in an excel sheet. Later they will be exported to the platform of the SPSS program. The variables will be categorized according to their nature.

CONFIDENTIAL

The result of the continuous quantitative variables will be presented in measures of central tendency: media, standard deviation and ranges. **See Table 5**. Scales to be used

The normal distribution of the results will be obtained by the Kolmogorov-Smirnov test.

The statistical analysis of the continuous **quantitative variables** to find significant differences (p) will be the following:

- Intra-group analysis: Wilcoxon rank test.
- Inter-group analysis: Kruskal-Wallis test.

The level of difference to consider significance will be an alpha of 0.05 or less.

The result of nominal and ordinal qualitative variables will be presented in frequencies, proportions and percentages. See table 1 (section 6.4.3).

The statistical analysis to identify significant differences of the **qualitative variables** will be done by creating 2x2 contingency tables and will be done as follows:

- • Intra-group difference: McNemar test.
- • Difference between groups: χ2 test (Chi-square) of Pearson.
- The level of difference to consider significance will be of an alpha of 0.05 or less.
- For the reporting of adverse events all eyes of those participants who were randomly assigned to an intervention group after the baseline visit will be considered. The results will be expressed in number of cases (eyes).
- The final report of the results will be shown in tables or graphs, as appropriate.
- It will be considered that the investigational drug is safe and tolerable when there are no clinical and statistical differences in all the variables of primary outcome, with respect to its comparators.

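### Pearson's chi-square in 2x2 tables does not reliably hold the stated 0.05 level, whether the tables count eyes or subjects

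*Combined protocol and SAP*

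**What the plan says.** Section 8.3.1 states that the analysis of qualitative variables "will be done by creating 2x2 contingency tables and will be done as follows". Within groups it names McNemar without saying which form. Between groups it gives "Difference between groups: χ2 test (Chi-square) of Pearson". The criterion is "The level of difference to consider significance will be of an alpha of 0.05 or less". The summary also names chi-square. No exact test, continuity correction or expected-count rule appears anywhere, and the plan does not say which pairs of the three arms form the 2x2 tables or how five-level variables are cut in two.

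The qualitative primary variables include adverse events, hyperaemia, chemosis, burning, foreign body sensation and itching (sections 6.4.1 and 6.4.3).

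On numbers, section 6.6.1 states that "the result is 7.6 subjects (8) per group", adds 25% for losses, and concludes that "each group will consist of 10 subjects, who will provide both eyes for the analysis", 60 eyes in all. Section 8.3.1 expresses adverse events as numbers of eyes, for everyone randomised. It limits the main analysis to adherence above 60%, and section 8.3.3 requires visits 1 and 2.

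Section 8.3.1 calls the product safe and tolerable when no primary variable shows clinical and statistical differences from the comparators.

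**The concern.** Pearson's p-value is a large-sample approximation, and the tables here are small. It also assumes that every unit counted is independent, which two eyes of one person are not. Which of these matters depends on the unit, and the plan sets out neither an adjustment for pairing nor a small-sample method.

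The level of each test bears directly on the trial's conclusion. A false difference on one primary variable can stand in the way of the safe-and-tolerable statement. A test with almost no chance of rejecting makes that statement easy to reach. If the true level ranges from well under 1% to above 10% according to event rate, arm size and correlation between eyes, results at 0.05 cannot be read the same way across variables.

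**Working it through.** **Inputs.** From the documents: alpha 0.05, two-sided (z = 1.96); 10 subjects or 20 eyes per arm; 8 per arm as the calculated size before losses; 8% adverse-event rate (section 6.6.1). Assumed: the inter-eye correlation ρ, for which the documents give no value, and common rates other than 8%.

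**The plan's own size.** The second proportion is not given as a number. The usual formula is (p1q1 + p2q2)(1.96 + 0.84)² / (p1 − p2)².
- 0.08 v 0.60: (0.0736 + 0.24) × 7.84 / 0.2704 = 9.09.
- 0.08 v 0.40: 0.3136 × 7.84 / 0.1024 = 24.0.
- 7.6 appears only with p2 = 0.64, which the text does not state.

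The 7.6 is therefore not reproduced. The step 24 × 1.25 = 30 is. Below, 8 serves only as the plan's own evaluable size.

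**Expected events per arm at 8%.** 8 × 0.08 = 0.64; 10 × 0.08 = 0.80; 20 × 0.08 = 1.6.

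**Level with subjects as units.** For arms n and m with common rate p, the true level is the sum, over all tables (a, b) with Pearson p ≤ 0.05, of Bin(a; n, p) × Bin(b; m, p). The peak over p is:

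| Arms | Peak true level |
|---|---|
| 10 v 10 | 4.2% |
| 8 v 10 | 5.3% |
| 9 v 9 | 5.7% |
| 9 v 10 | 6.5% |
| 8 v 8 | 7.7% |

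At 8 v 8 the level passes 5% only from a common rate of about 29%: it is 0.2% at 8%, 2.7% at 20%, 5.3% at 30% and 7.7% at 50%. At the 8% rate all five pairs lie between 0.2% and 1.6%.

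One table shows the effect. For 1/8 v 5/8, X² = 16 × (1×3 − 7×5)² / (8×8×6×10) = 16 × 1024 / 3840 = 4.27. Pearson gives p = 0.039, Boschloo 0.053 and Fisher 0.119.

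**Level with eyes as units (20 v 20).** For each subject, P(both eyes affected) = p² + ρp(1−p) and P(exactly one) = 2p(1−p)(1−ρ). Ten subjects are summed per arm and the same rejection rule is applied.
- ρ = 0: 2.9% at an 8% rate; peak 5.3%.
- ρ = 0.3: 5.4% to 9.1% for rates of 8% to 50%.
- ρ = 0.5: 7.4% at 8%, 11.6% at 20%, 11.7% at 30%.
- ρ = 1: up to about 22%.

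As a rough check, pairing multiplies the variance of an arm's count by 1 + ρ. At ρ = 0.5 the effective cut-off is 1.96/√1.5 = 1.60, a two-sided level of about 11%.

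**Alternatives, subjects as units, power at 8% v 60%.**

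| Test | 10 v 10: peak level, power | 8 v 8: peak level, power |
|---|---|---|
| Pearson | 4.2%, 0.71 | 7.7%, 0.67 |
| Boschloo | 4.2%, 0.71 | 2.8%, 0.55 |
| Fisher | 1.3%, 0.53 | 2.1%, 0.43 |

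At 10 v 10 Boschloo and Pearson reject exactly the same tables. Fisher applied to 20 eyes per arm does not solve the pairing problem: at ρ = 0.5 its level is 5.7% to 6.9% for rates of 15% to 50%.

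**McNemar.** With five discordant pairs all in one direction, X² = 5²/5 = 5 and p = 0.025 uncorrected. With continuity correction, 4²/5 = 3.2 and p = 0.074. The exact form gives 2 × 0.5⁵ = 0.0625. The unstated choice decides significance.

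**The case against.** The strongest reply is that the plan analyses eyes, so tables of 8 to 10 are not the ones planned, and that at 20 v 20 Pearson peaks at 5.3%. The arithmetic is right, but it requires uncorrelated fellow eyes, so it does not rescue the stated level.

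Three further replies stand and limit the point.
- Inflation on subjects needs losses and mid-range rates. These are healthy volunteers, and the documents give no rates for the signs or symptoms. Mid-range rates can be neither excluded nor assumed.
- Adverse events keep everyone randomised, so losses do not shrink that table. Counted as subjects it is 10 v 10, where Pearson stays below 5%.
- A more conservative test makes the safe-and-tolerable statement easier to reach. This is a sound reason against Fisher as the default.

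A reader might infer that chi-square at this size generally produces too many false alarms. The documents do not support that: on subjects at the plan's own 8% rate the test is far too conservative. A reader might also attribute to chi-square the 13.7% chance of at least one false difference when PRO-087 is tested against two comparators at 8 per arm. That figure needs a common rate of 50% and is mostly multiplicity: two independent tests at exactly 5% already give 1 − 0.95² = 9.75%. Finally, the plan does not say that McNemar is asymptotic. The defect there is an unspecified form, and the within-group test does not enter the comparison with comparators.

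**Conclusion.** The point holds in limited form. Section 8.3.1 relies on one large-sample test that does not reliably deliver 0.05 on either unit. The larger upward error is on eyes, about 7% to 12% at ρ = 0.5, and it rests on that assumed correlation. The subject-level excess is modest, with peaks of 5.3% to 7.7%; it arises only after losses and, at 8 v 8, only for common rates of about 29% or more. The downward error at low rates, 0.2% to 1.6% on subjects, follows from the plan's own 8% rate.

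This is an inexpensive correction to an exploratory phase I plan. It is secondary to two matters that a change of test does not address: multiplicity across variables and comparators, and the reading of non-significance as evidence of safety.

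**What to change.** In section 8.3.1:

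- Reduce each qualitative variable to one outcome per subject, stating in advance how the two eyes are combined (for example, either eye affected) and where graded variables are cut.
- Compare PRO-087 with each comparator by Boschloo's exact unconditional test, naming both comparisons.
- Specify the exact binomial form of McNemar.
- Report exact 95% confidence intervals for each arm's proportion beside the p-values. At low event rates these tell the reader more than any of the tests, since an exact test does not restore a 5% level there.
- Do not make Fisher the default: its true level peaks at only about 1–2.5% for the arm sizes tabulated above.

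The cost is protocol wording and a few lines of code, possibly outside the named package (SPSS 19). No visit, measurement or sample-size change is needed. Relative to Pearson on subjects, Boschloo changes nothing at 10 v 10 and loses some power in smaller arms (0.55 against 0.67 at 8 v 8 for 8% v 60%).

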#### 6.4 Outcome variables.

#### 6.4.1 Security variables.

#### 6.4.1.1 Primary outcome variables.

- Density of goblet cells
- Presence of adverse events.
- Intraocular pressure.
- Visual ability
- Laboratory tests: BHc, QS and PFH.
- Epithelial defects in cornea and conjunctiva.
- Ophthalmological signs: conjunctival hyperemia, chemosis.

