#### 6.4.3 Methods and scales to be used for the measurement of the variables

Variable	Unity	Symbol	Туре	Method of measurement	Normal value
Age	Years		Continuous	Calculation from the date of birth	NA
Gender	Female Male	F / M	Nominal	Direct questioning	NA
Adverse events	Number of cases	n	Discreet	Count	NA
Intraocular pressure	Milimeters of mercury	mmHg	Continuous	Goldman's applanation tonometry	11 - 21
Visual ability	Fraction	Snellen	Nominal	Primer	
Tear rupture time	Seconds	S	Continuous	Direct count	> 10
Eye comfort index	points		Discreet	Questionnaire	
Adverse events	Present / Absent		Nominal	Comprehensive valuation	Absent
Goblet cell density	Cells per square millimeter	Cel/mm 	Continuous	Cytology by impression	> 500 cel/mm 
Vital signs					
Heart rate	Beats per minute	lpm	Discreet	Auscultation	60 - 100
Breathing frequency	Breaths per minute	rpm	Discreet	Auscultation	12 – 24
Systemic blood pressure	Milimeters of mercury	mmHg	Continuous	Non-invasive auscultatory measurement	< 120 / 80
Previous segment					
Epithelial defects	Degrees		Discreet	Direct observation with fluorescein and green lysamin stain	Oxford Scale

Sophia Laboratories, S.A. of C.V.

Variable	Unity	Symbol	Туре	Method of measurement	Normal value
Ophthalmologic signs ar	nd symptoms				
Conjunctival hyperemia	Normal / Very Light / Mild / Moderate / Severe		Ordinal	Direct observation. Classification of Efron.	Normal
Chemosis	Present / Absent		Nominal	Direct observation	Absent
Burning	Severity: Absent, very mild, mild, moderate and severe		Nominal	Direct questioning	Absent
Foreign body sensation	Severity: Absent, very mild, mild, moderate and severe		Nominal	Direct questioning	Absent
Pruritus	Frequency: At all times, almost at all times, 50% of the time, almost in no time, at any time		Nominal	Direct questioning	Absent
Postinstilation symptoms	5				
Burning	Present / Absent		Nominal	Journal of the subject	Absent
Foreign body sensation	Present / Absent		Nominal	Journal of the subject	Absent
Pruritus	Present / Absent		Nominal	Journal of the subject	Absent
Red eye (symptom)	Present / Away		Nominal	Journal of the subject	Absent

Sophia Laboratories, S.A. of C.V.

Variable	Unity	Symbol	Туре	Method of measurement	Normal value
Posterior segment					
Magula	Normal /				
Macula	Abnormal		Nominal	Observación directa	Normal
Optical disk integrity	Normal / Abnormal		Nominal	Observación directa	Normal
Blood count					
Erythrocytes		M/uL	Continuous		

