#### Security call / Day 13.

It can be done in a period  $\pm 1$  day in relation to the 13th day of the start of application.

- 1. Ask about the presence of an adverse event.
- 2. Evaluation of results of laboratory tests

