#### 9.3.1.1 Record of adverse events in the Case Report Form

The registry of adverse events considers the information concerning the identification data of the participating patient as code, age, sex, left eye, right eye.

Information about the type of adverse event, adverse reaction or suspected adverse reaction to the product under investigation or to the study medication, as appropriate. The date on which the adverse event occurs is reported, as well as in which the Investigator is aware of it, date of resolution or outcome, as applicable. The clinical diagnosis is indicated. Include in concomitant medications the therapy used for the pharmacological management of the adverse event, suspected adverse reaction, adverse reaction. Record the outcome or resolution of the event: patient recovered without sequelae, with sequelae, not recovered. Patient who presented death due to adverse reaction / adverse event, patient who presented death and it is judged that the drug could have contributed, patient who presented death and this is not related to the investigational product or drug, or indicate that it was not knows what the consequence of the event is.

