The record of the outcome of the adverse event, suspicion of adverse reaction or adverse reaction to medication depends substantially on the follow-up that the principal investigator makes to the participant, since most of the harmful phenomena are expected, consult section of the safety profile in number 5.3 and in the researcher's manual, they are ophthalmic in nature, nevertheless there may be systemic alterations. Therefore, in the opinion of the researcher, the withdrawal of the participant or his / her permanence will be considered, according to the stipulations of section 6.2.2 Exclusion criteria of the present research protocol.

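### Adverse events are reported and compared in eyes, with no rule for how a non-ocular event enters the eye count

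*Combined protocol and SAP*

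**What the plan says.** Section 6.4.1.1 lists "Presence of adverse events" among the primary safety variables, without restricting it to the eye. In section 8.3.1, the sentence that sets the basis for reporting begins: "For the reporting of adverse events all eyes of those participants who were randomly assigned to an intervention group after the baseline visit will be". The section then gives the unit: "The results will be expressed in number of cases (eyes"). The same section compares qualitative variables between groups by Pearson chi-square on 2x2 tables. It treats the product as safe and tolerable only if no primary variable differs from the comparators.

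Other sections bear on the unit:

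- Section 9.3.1.3 says of the harmful phenomena that are mostly expected: "they are ophthalmic in nature, nevertheless there may be systemic alterations".
- Section 9.3.1.1 has the event record carry "identification data of the participating patient as code, age, sex, left eye, right eye", together with the type of event and the clinical diagnosis. It describes no category for an event outside the eye.
- Table 5 in section 6.4.3 lists adverse events twice: once as "Number of cases", obtained by counting, and once as present or absent. Neither row names the eye or the subject.
- Section 9.2 writes the serious-event criterion for early termination as a percentage of participants in each group.

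**The concern.** An eye count suits a red eye or a corneal defect. It does not suit a headache or a non-ocular serious event, which belongs to neither eye. Under section 8.3.1 such an event could be left out, entered once or entered for both eyes, and each choice is compatible with the text. The variable is primary and feeds the rule for calling the product safe and tolerable, so the choice could change the trial's conclusion. If it is left until analysis, it can be made with the results in view.

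The partial analysis is also affected. Section 8.3.2 applies the same mechanisms after 3 subjects per group, and section 9.2 uses that analysis in deciding on early termination. A table in eyes does not directly give the participant numerator that section 9.2 needs.

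**Working it through.** **Denominators (section 6.6.1).** 8 per group x 3 = 24; 24 x 1.25 = 30 subjects, or 10 per group; 30 x 2 = 60 eyes, or 20 per group. These reproduce the plan's figures.

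**One non-ocular event in one arm.**

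- By subject: 1/10 = 10%.
- By eye: 0/20 = 0% if unassigned, 1/20 = 5% if scored once, 2/20 = 10% if scored in both eyes.
- At the partial analysis (3 subjects, 6 eyes per arm): 1/3 by subject, but 0/6, 1/6 or 2/6 by eye.

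**Effect on the planned test.** The documents give no systemic event rate, so the counts here are assumptions: *a* of 10 subjects affected in one arm and 0 of 10 in another. For a 2x2 table with cells A, B, C, D, row totals r1, r2, column totals c1, c2 and overall total N, Pearson chi-square without correction is N(AD - BC)² / (r1 r2 c1 c2). The 5% critical value on 1 degree of freedom is 1.96² = 3.84.

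For *a* = 2:

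- By subject, 2/10 v 0/10: 20 x (2x10 - 8x0)² / (10x10x2x18) = 8000/3600 = 2.22, p = 0.136.
- Each event in one eye, 2/20 v 0/20: 40 x (2x20 - 18x0)² / (20x20x2x38) = 64000/30400 = 2.11, p = 0.147.
- Each event in both eyes, 4/20 v 0/20: 40 x (4x20 - 16x0)² / (20x20x4x36) = 256000/57600 = 4.44, p = 0.035.
- Unassigned, 0/20 v 0/20: nothing to compare.

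For *a* from 1 to 4:

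| Subjects affected (v 0 of 10) | p by subject | p, one eye each | p, both eyes |
|---|---|---|---|
| 1 | 0.305 | 0.311 | 0.147 |
| 2 | 0.136 | 0.147 | 0.035 |
| 3 | 0.060 | 0.072 | 0.008 |
| 4 | 0.025 | 0.035 | 0.002 |

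At 2 or 3 affected subjects, the pairwise result at 0.05 differs between the subject count and the both-eyes count. In a three-arm table with the events in one arm only, the split occurs at 2 affected subjects (0.117 by subject, 0.126 one eye, 0.014 both eyes). At 3, all three scorings fall below 0.05 (0.0357, 0.0425, 0.0013). The unassigned reading shows no signal at any count.

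Scoring both eyes leaves the percentage unchanged but doubles every cell, and so doubles chi-square (2.22 to 4.44). With *a* = 2 by subject, the expected number of events per arm is only 2 x 10 / 20 = 1. The p-values therefore show what the planned test would return; they are not accurate error probabilities.

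**The case against.** The strongest reply is that the events are neither lost nor impossible to record. Both adverse-event rows in Table 5 are neutral as to unit and can hold a headache. The case report form takes the type of event and the diagnosis (9.3.1.1). Serious events are notified within 24 hours and non-serious ones are recorded (9.3.1.3). The final report includes adverse events (9.3.1). A non-ocular serious event still counts towards the participant-based criterion in section 9.2. All of this stands. A reader might infer that systemic events cannot be scored or will vanish from the trial, but the documents do not support that. Omission and double counting are possible readings that the plan does not state.

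A reader might also infer that abnormal laboratory results fall out of the safety assessment. They do not. "Laboratory tests: BHc, QS and PFH" is a separate primary safety variable. "Evaluation of results of laboratory tests" is listed at the day 13 call apart from the adverse-event question, and no section makes an abnormal result an adverse event.

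Nor does the protocol expect systemic events. It expects mainly ophthalmic ones and says that systemic ones may occur. Section 5.3 reports no corneal absorption of either active ingredient, so such events may be few.

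Finally, the harm from scoring both eyes overlaps with the general problem of treating a subject's two eyes as independent. That is fair for this one reading. A correction for the correlation between eyes would still not say whether, or where, a non-ocular event is counted.

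**Conclusion.** The point holds as a fault in the analysis unit. Section 8.3.1 fixes the eye as basis and unit for a primary variable that is not limited to the eye. Table 5 names no unit, section 9.2 uses participants, and no section connects the three for a non-ocular event. One affected subject in an arm of 10 can read as 0%, 5% or 10% of eyes. With 2 of 10 against 0 of 10, p is 0.136, 0.147 or 0.035, or there is no comparison at all.

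These p-values rest on assumed counts and on the uncorrected Pearson test. The frequency of systemic events cannot be estimated from the documents. The 8% in section 6.6.1 is an overall adverse-event rate from a cited 3-month study, with no systemic share given, so it does not measure this problem. If no non-ocular event occurs, nothing changes. If any occurs, the reported rate depends on a rule that has not been written. The change should be made before any data are analysed, including the partial analysis.

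**What to change.** In section 8.3.1, replace the eye unit for adverse events with the following: adverse events are reported and compared as number and percentage of subjects with at least one event, together with the number of events, per arm, with all randomised subjects as denominator. Show ocular and non-ocular events in separate rows. Give eye counts only as a descriptive supplement for ocular events. Name the same unit in the adverse-event rows of Table 5, and let section 8.3.2 inherit it.

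This brings the adverse-event tables into the participant unit already used in section 9.2, whose criterion is not altered. It needs no new data, because section 9.3.1.1 already records subject code, eye and diagnosis. The cost is a reworded sentence, an extra table row and a smaller denominator: 10 subjects per arm in place of 20 eyes.

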# 5.5.3 Hypothesis

Ha The ophthalmic solution PRO-087 presents a safety and tolerability profile similar to comparators in healthy subjects

*Ho The ophthalmic solution PRO-087 presents a different safety and tolerability profile compared to comparators in healthy subjects.* 

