#### 6.4.3.12 Lab tests.

The PI will deliver to the subject the order of the studies of BH, QS and PFH, to be carried out in the clinical laboratory designated by the sponsor. The clinical laboratory will deliver to the IP the results for its assessment and registration. The normal parameters to be considered will be the ranges established by the laboratory, Nevertheless the clinical criterion of the PI will prevail in the decision of normality or abnormality of the results.

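### Section 8.3.1 treats the absence of significant differences as proof that PRO-087 is safe and tolerable, but tests of equality with no margin, interval criterion or defined clinical difference cannot support that conclusion

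*Combined protocol and SAP*

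**What the plan says.** Section 8.3.1 sets a formal rule: "the investigational drug is safe and tolerable when there are no clinical and statistical differences in all the variables of primary outcome", with respect to the comparators. Section 5.5.3 states "Ha The ophthalmic solution PRO-087 presents a safety and tolerability profile similar to comparators in healthy subjects" and makes a differing profile the null.

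The between-group methods in section 8.3.1 are "Inter-group analysis: Kruskal-Wallis test" for quantitative variables and Pearson chi-square for qualitative ones, where the analysis "will be done by creating 2x2 contingency tables". Each is run at alpha 0.05. For adverse events, "The results will be expressed in number of cases (eyes"), and section 6.6.1 says that both eyes of each subject enter the analysis, "so that the total sample to be analyzed will be composed of 60 eyes".

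The primary variables number seven for safety (section 6.4.1.1) and four for tolerability (section 6.4.1.2). On what counts as a clinical difference, Table 5 in section 6.4.3 lists normal values for individual subjects, and section 6.4.3.12 says of laboratory tests that "the clinical criterion of the PI will prevail in the decision of normality or abnormality of the results". Neither is a criterion for comparing groups. The only margin in the document is the 10% tolerance on laboratory ranges for eligibility (section 6.2.1).

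**The concern.** The hypothesis pair has the form of an equivalence question: the burden is to show similarity. The planned tests carry the opposite burden, since they presume equality and look for evidence against it. No planned test can reject the null hypothesis in section 5.5.3, so a non-significant result leaves similarity unproven. In a small trial, non-significance is the likely outcome across a wide range of true differences.

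The word clinical in the rule might have repaired this, but it has no threshold for any primary variable. The phrase is also ambiguous: failure might need either kind of difference, or both together. Neither reading can be checked before or after unblinding.

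At stake is the trial's main conclusion. A report could state that PRO-087 is safe and tolerable on data compatible with a large excess of adverse events.

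**Working it through.** **The plan's own figure.** The plan gives no operating characteristic for the decision rule, only a sample size of 7.6 per group. The usual two-proportion formula is n = [p1(1-p1) + p2(1-p2)](1.96 + 0.84)² / (p1 - p2)².
- p1 = 0.08, p2 = 0.60: (0.0736 + 0.2400) × 7.84 / 0.2704 = 9.09.
- p1 = 0.08, p2 = 0.64: (0.0736 + 0.2304) × 7.84 / 0.3136 = 7.60. The value 0.64 is not stated in the plan.

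Either way, the trial is sized to detect a very large difference, not to show similarity.

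**Inputs.** 10 subjects (20 eyes) per arm and alpha 0.05 are from the plan. Section 6.6.1 states "The percentage of adverse events that occurred with the preservative-free HS solution was 8" per cent. Applying that 8% to both comparators, per subject or per eye, is my assumption. So are the 30% for PRO-087 and the within-subject correlations. The 60% echoes a figure in section 6.6.1 whose meaning is unclear.

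**A worked result, with no true rate assumed.** Suppose 3/10 subjects on PRO-087 and 1/10 on a comparator have events, each in both eyes.
- Subjects, 3/10 against 1/10: chi-square = 1.25 on 1 df, p = 0.26.
- Eyes, 6/20 against 2/20: chi-square = 2.50 on 1 df, p = 0.11.
- Eyes, three groups, 6/20, 2/20, 2/20: chi-square = 3.84 on 2 df, p = 0.15.
- 95% interval for the subject-level difference (Newcombe). The Wilson limits are 0.108 to 0.603 and 0.018 to 0.404. Lower: 0.20 - √[(0.30 - 0.108)² + (0.404 - 0.10)²] = -0.16. Upper: 0.20 + √[(0.603 - 0.30)² + (0.10 - 0.018)²] = +0.51.

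The statistical part of this item is met, yet an excess of 51 points is not excluded. With 0/10 events, the two-sided 95% upper limit is 1 - 0.025^(1/10) = 31%.

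**How often the adverse-event test is non-significant.** These are exact enumerations of the uncorrected Pearson test, with comparators at 8%. For eyes, P(both affected) = p² + ρp(1-p). The plan prescribes 2x2 tables for three groups, so three layouts are shown: one 2x2 / neither of two 2x2 significant / one 3x2.

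| Unit | PRO-087 at 30% | PRO-087 at 60% |
|---|---|---|
| Subjects | 82.8 / 74.8 / 72.9% | 28.8 / 16.4 / 18.4% |
| Eyes, ρ = 0 | 56.0 / 39.9 / 52.3% | 2.9 / 0.8 / 1.4% |
| Eyes, ρ = 0.5 | 53.3 / 37.2 / 48.1% | 6.0 / 1.8 / 3.1% |
| Eyes, ρ = 1 | 46.9 / 30.5 / 44.4% | 7.2 / 2.3 / 5.1% |

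Counting eyes raises the chance of significance partly by ignoring the pairing. With identical products at 8%, this one item is falsely significant 2.9 / 5.4 / 3.8% of the time at ρ = 0, 7.4 / 13.0 / 10.9% at ρ = 0.5 and 16.8 / 28.2 / 16.6% at ρ = 1.

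**Quantitative variables.** In a simulation with 10 per group and normal data (4,000 runs), Kruskal-Wallis missed a 1 SD shift in one arm 45% of the time and a 0.5 SD shift 83% of the time.

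**The opposite error.** If any statistical difference counts as failure, 11 independent tests each at exactly 5% flag an identical product 1 - 0.95^11 = 43% of the time.

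**The case against.** The strongest reply is that this is an exploratory phase I study (section 5.6) whose specific objectives are all worded as descriptions (section 5.5.2). The Summary's statistical section carries no decision rule. Participant protection rests on the partial analysis, the termination criteria and the adverse-event procedures (sections 6.5.2, 8.3.2, 9.2 and 9.3), not on this sentence. All of that stands and lowers the severity. It does not rescue the rule, because section 8.3.1 still sets a verdict that those descriptive objectives do not need.

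The test is also not weak everywhere: at 60% on PRO-087, non-significance falls to 16-29% on subjects and 1-7% on eyes. That stands too. The weakness concerns smaller but still important excesses.

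Three stronger readings are tempting, and the documents do not support them.
- *A product with a 30% event rate would be declared safe 30-56% of the time.* Those figures are the chance of a non-significant result on one of 11 items. The rule requires all of them, and the clinical limb could still fail the product. If the other ten items were independent, truly equal and tested at 5%, the range would shrink by 0.95^10 = 0.599, to about 18-34%. The true overall rate cannot be computed from the documents.
- *The false-failure rate is at most 43%.* It is not a bound. Ten items at 5% and one at 28.2% give 1 - 0.599 × 0.718 = 57%, and the single laboratory item covers 25 analytes in Table 5 (17 + 3 + 5).
- *A stricter alpha would help.* It would reduce false failure but make a false declaration of safety easier.

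**Conclusion.** The rule is wrong as written and should be fixed. Non-significance on tests of equality cannot establish the similarity that section 5.5.3 calls the alternative, and nothing else in the plan supplies a checkable criterion. This conclusion is a matter of logic and rests on no assumed rate.

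The size of the problem is best shown by the worked result: p = 0.26, with an interval from -16 to +51 points. The probabilities of 73-83% (subjects) and about 30-56% (eyes) depend on 8% in the comparators, an assumed 30% on PRO-087, and within-subject correlations from 0 to 1. The 43% is an illustration that depends on independence and on exact 5% tests.

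A reader might infer that the flaw exposes participants to harm or invalidates the study. The documents do not support that. The group data will still be tabulated, and the damage is confined to what the final report claims.

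**What to change.** Delete the decision sentence in section 8.3.1 and the hypothesis pair in section 5.5.3. Replace them with text such as: for each primary variable, the difference between PRO-087 and each comparator will be reported with a 95% confidence interval that treats the subject as the independent unit; no conclusion of similarity, safety or tolerability will be drawn from a non-significant p value; the conclusion is descriptive. This agrees with the exploratory label and the descriptive objectives. Section 6.6.1 would then need a line saying what its power calculation serves.

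No extra subjects or visits are needed. The costs are the loss of the automatic claim and a protocol amendment with committee review and regulatory authorisation (section 10.2).

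If the sponsor wants a similarity claim, it must fix and justify a margin before unblinding. With 10 per arm only a wide margin could be met: even 0/10 against 0/10 gives a 95% interval of about ±28 points.
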